6.3.2 Spinal Cord Independence Measure

The Spinal Cord Independence Measure (SCIM) III will be assessed. SCIM III results at Baseline Visit will be used as the reference time point to assess changes in subjects' quality of life at the follow-up visits. The Spinal Cord Independence Measure (SCIM) III covers 19 tasks, all activities of daily living, grouped into four areas of function: Self-Care (Questions 1-4, scored 0-20), Respiration and Sphincter Management (Questions 5-8, scored 0-40), Mobility in Room and Toilet (Questions 9-11) and Mobility Indoors and Outdoors on Even Surface (Questions 12-17) (Mobility Questions 9-17, Scored 0-40). The final total SCIM III is the sum of all scores and score ranges from 0 to 100, with 0 being requiring total assistance and 100 being completely independent.

SCIM III total score and each domain score, with changes from baseline, will be summarized at each visit for the overall Intent to Treat Population.

6.3.3 Lower Urinary Tract Function

Lower urinary tract function will be assessed using the questionnaire from the International Spinal Cord Injury Data Sets – Lower Urinary Tract Function Basic Data Set – Data Form. The lower urinary tract data will be listed, and any changes from baseline, where the 1 Month Visit is considered the baseline visit, will be assessed qualitatively.

6.3.4 **Bowel Function**

Bowel function will be assessed using the questionnaire from the International Spinal Cord Injury Data Sets – Bowel Function Basic Data Set – Data Form. The bowel function data will be listed, and any changes from baseline, where the 1 Month Visit is considered the baseline visit, will be assessed qualitatively.

6.3.5 The Graded Redefined Assessment of Strength, Sensibility and Prehension

The Graded Redefined Assessment of Strength, Sensibility and Prehension (GRASSP) is a multimodal test comprising 5 subtests on the left and right side for each upper limb: dorsal sensation (3 subscores 0-4; total 0-12 for each side), palmar sensation (3 subscores 0-4; total 0-12 for each side), strength (tested with motor grading of 10 muscles 0-5; total 0-50 for each side), qualitative prehension (3 tasks 0-4; total 0-12 for each side), and quantitative prehension (6 tasks scored 0-5; total 0-30). Baseline GRASSP scores will be taken from the Baseline visit. A higher score represents improvement while a lower score represents worsening.

GRASSP subscores and subtest total scores will be presented in listings, where applicable. GRASSP subtest total scores for Total Strength (0-100), Total Quantitative Prehension (0-60), and Total Sensation (0-48), with changes from baseline (where the Baseline Visit on Day -2 to -1 will be considered the baseline), will be summarized at each visit for the overall Intent to Treat Population. Total Qualitative Prehension (0-24) summary statistics will be presented at each visit without change from baseline due to different baseline study visits across protocol amendments.

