A key safety consideration for patients with a C4 NLI is that an ascending neurological level (i.e., to C3 or higher) could result in a loss of one's ability to breathe without the assistance of a ventilator. To date, a total of 17 subjects have received AST-OPC1 in this study, and no subject has had an ascending NLI following AST-OPC1 administration. In addition, of the 12 subjects who have reached the six-month follow up visit, 11 have improved at least one motor level on at least one side relative to baseline and 1 has a stable motor level relative to baseline. In order to provide an additional margin of safety, patients with a C4 NLI must have an UEMS \geq 1 in order to be eligible for this study and a staggering rule has been added for Cohorts 2-5 that requires a 14-day stagger between the dosing of any two consecutive subjects who have a C4 NLI.

Rationale for changing the dosing window to 21-42 days post-SCI

The current dosing window of 14-30 days was selected to avoid the early hemorrhage and inflammation that occurs following SCI, as well as the scar tissue formation that occurs in the chronic phase of SCI. This window was also based on the preclinical data available prior to the initiation of this clinical study. However, Asterias recently completed a new preclinical study to further evaluate the appropriate dosing window for AST-OPC1, and the findings from this study suggest that the optimal dosing window in human subjects may extend to at least 60 days post-SCI (see Investigator's Brochure for details).

Asterias reviewed these new preclinical data with the current study investigators and several SCI experts to determine whether the dosing window should be adjusted. Consideration was also given to the planned inclusion of patients with a C4 NLI. Based on these reviews, it was determined that a dosing window of 21-42 days post-SCI would still be squarely within the subacute period but would also allow more time for patients to be medically stable prior to undergoing elective surgery for AST-OPC1 administration.

Amendment 2: 03 May 2016

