9	Rationale for AST-OPC1 Administration in Subacute SCI: Updated to reflect the new dosing window, which is supported by new preclinical data that is provided in the accompanying revision to the Investigator's Brochure	Section 1.3.3
10	Complications of Spinal Cord Injury: Added a section that lists these complications to clarify which adverse events would be expected due to the fact	Section 1.4.1

	that all subjects suffered an SCI prior to study entry	
11	Surgical Injection Procedures: Updated to note that one of the risks is hemorrhage and/or fluid collection in tissues between the incision site and the spinal cord	Section 1.4.2
12	AST-OPC1 Administration: Added recommendations for placement of an arterial line in all subjects and for intraoperative monitoring of somatosensory evoked potentials in AIS-B subjects based upon consultation with several study investigators and surgeons	Section 6.4
13	Tests and Observations: Deleted testing for ionized calcium based on the recommendation of a clinical expert and because several site labs were unable to perform this test, which resulted in several protocol deviations. In addition, there have been no clinically significant abnormalities of ionized calcium in any subject to date.	Section 7 (all subsections in which blood chemistry testing is performed)
14	Tests and Observations: Deleted the GRASSP test from post-injection Day 30 and added the GRASSP test to post-injection Day 90 based on the advice of our expert consultant for GRASSP	Sections 7.7, 7.10; Table 7-1
15	Tests and Observations: Deleted the fasting blood glucose test at post-injection Day 60 because subjects receive extremely low doses of tacrolimus during the Day 46-60 taper period and because there have been no clinically significant abnormalities for this test in any subject to date	Section 7.9; Table 7-1
16	Efficacy Analyses: Corrected two typographical errors	Section 9.3.2

E.

LIST OF ABBREVIATIONS AND DEFINITION OF TERMS

Abbreviation	Definition
or term	
AIS	ASIA Impairment Scale
ALI	alanine aminotransferase
ASIA	American Spinal Injury Association
AST	aspartate aminotransferase
AST-OPC1	investigational product (formerly GRNOPC1)
BBB	Basso, Beattie, and Bresnahan behavior locomotor score
BUN	blood urea nitrogen
CFR	Code of Federal Regulations
CNS	central nervous system
CSF	cerebral spinal fluid
DLT	dose-limiting toxicity
DMC	Data Monitoring Committee
DTPA	diethylenetriamine pentaacetic acid
ECG	electrocardiogram
eCRF	electronic case report form

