3.2.1 Sample Size Considerations

A total of 23-35 subjects were planned to receive AST-OPC1. Enrollment concluded on December 15, 2017 and a total of 25 subjects were enrolled and received AST-OPC1 across the five cohorts:

- Cohort 1: 3 Subjects
- Cohort 2: 6 Subjects
- Cohort 3: 6 Subjects
- Cohort 4: 6 Subjects
- Cohort 5: 4 Subjects

The sample size is based on the study design considerations for a Phase 1/2a study. This trial employs a cross-sequential cohort design for Phase 1 dose escalation in cervical AIS-A and AIS-B subjects. Power calculations have not been performed, as the primary objective is to collect safety and tolerability information on a limited number of subjects per dose level and AIS Grade, and an effect size cannot yet be estimated.

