5. STATISTICAL ANALYSIS GENERAL CONSIDERATIONS

5.1 Analysis Populations

Screened Population

The Screened Population will include all subjects who completed an informed consent form. This will be used for the purposes of summarizing disposition.

All Treated Population

The All Treated Population will include all subjects who received an injection of AST-OPC1. This will be used for all safety analyses.

Intent to Treat Population

The Intent to Treat Population will include all subjects who received an injection of AST-OPC1 in Cohorts 2 through 5. This population will be used for all efficacy analyses, and results will be presented for the overall, aggregated population.

Not Treated Population

The Not Treated Safety Population will include all subjects who have pharmacological deep vein thrombosis prophylaxis withdrawn in preparation for the surgery, but do not receive AST-OPC1. This population will have safety data collected for 30 days.

A topline summary of Adverse Events will be presented for the Not Treated Population, and no further data summaries will be presented for this population. The Not Treated Population will have the data listed with the Screen Failure subjects, separately from the All Treated Population.

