5.3 Procedures for Handling Missing Data and Outliers

Missing or incomplete dates will be imputed per Section 6.2.2 for the purposes of determining treatment emergence. All other missing data will not be imputed, unless otherwise noted.

All unscheduled visit data will be included in data listings. In the data summary tables, the presence of missing data will be indicated by the inclusion of a 'missing' category with categorical data, and a count and percentage of missing observations for continuous numeric data, where applicable.

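### GRASSP moved from Day 30 to Day 90 at Amendment 3, so the pooled Day 90 summary in SAP 6.3.5 rests on a later-enrolled subset (at least 9 of 22 subjects had no such test scheduled) and is not like-for-like with Day 180

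*SAP*

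**What the plan says.** Under SAP 6.3.5, three GRASSP totals (strength, quantitative prehension, sensation), with changes from baseline, "will be summarized at each visit for the overall Intent to Treat Population". Total qualitative prehension is also summarised at each visit, but without change from baseline, because its baseline visit differed between protocol amendments. That is the only allowance the section makes for amendments. SAP 5.1 defines the population: "The Intent to Treat Population will include all subjects who received an injection of AST-OPC1 in Cohorts 2 through 5". It also says that results are presented for the aggregated population, and SAP 5.5 rules out subgroup analyses.

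The schedules in protocol Table 7-1 and SAP Table 2 place GRASSP at baseline and Days 90, 180, 270 and 365. Item 14 of the Amendment 3 summary of changes records how that came about: "Deleted the GRASSP test from post-injection Day 30 and added the GRASSP test to post-injection Day 90". The Amendment 3 rationale gives enrolment at the time: "To date, a total of 17 subjects have received AST-OPC1 in this study". It then reports motor-level results "of the 12 subjects who have reached the six-month follow up visit". Protocol 11.3 lets an amendment take effect only once IRB/IEC approval is documented.

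For missing values, SAP 5.3 imputes nothing here and displays "a count and percentage of missing observations for continuous numeric data, where applicable". It has no category for an assessment that was not scheduled under the protocol version then in force.

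**The concern.** Subjects who passed Day 90 before Amendment 3 had their early GRASSP planned for Day 30, not Day 90. A rule that summarises every visit for the whole efficacy population therefore uses a later-enrolled subset at Day 90 and potentially everyone at Day 180. Read down the table, the step from Day 90 to Day 180 looks like a gain or loss of hand function, yet part of it comes from adding the earlier subjects. With pooled results only, the table cannot separate the two.

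There are two lesser consequences. A planned change of schedule could be displayed as a large proportion of missing data at Day 90. The SAP also does not say whether the Day 30 GRASSP results from earlier subjects are to be tabulated.

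**Working it through.** The amendment log is used here only as evidence of which visits earlier subjects had, not as a conflict with current text.

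**Inputs**
- SAP 3.2.1: "a total of 25 subjects were enrolled and received AST-OPC1 across the five cohorts", with cohort sizes 3, 6, 6, 6 and 4 (the first being "Cohort 1: 3 Subjects").
- Amendment 3 rationale: 17 dosed, 12 at six months.
- Amendment 3 date: 07 July 2017. Visit windows: Day 90 ± 7, Day 180 ± 14.

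**1. Reproduce the stated total.** 3 + 6 + 6 + 6 + 4 = 25, as stated. Efficacy population: 25 − 3 = 22.

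**2. Had the 12 passed Day 90 before the amendment?** A Day 180 visit on 07 July 2017 could fall as early as Day 166 (180 − 14), so dosing was no later than 22 January 2017. The latest in-window Day 90 visit (Day 97) was then 29 April 2017, before the amendment date.

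**3. Lower bound on subjects with no Day 90 GRASSP scheduled.** Suppose all 3 Cohort 1 subjects are among the 12, which gives the smallest answer: 12 − 3 = 9, and 9/22 = 40.9%. At most 22 − 9 = 13 (59.1%) can contribute at Day 90.

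**4. Plausible upper figure.** Efficacy subjects among the 17 dosed: 17 − 3 = 14. If none of the other 14 − 9 = 5 had a Day 90 visit under Amendment 3, then 14/22 = 63.6% were unscheduled and 22 − 14 = 8 contribute. The unscheduled count would be higher still if anyone dosed between that count and site approval also missed the new test.

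**5. Effect on the pooled means.** Let k be the number unscheduled, S the mean of the scheduled subjects and U the mean of the unscheduled, with complete follow-up.
- Pooled Day 90 mean = S₉₀.
- Pooled Day 180 mean = [(22 − k)·S₁₈₀ + k·U₁₈₀]/22 = S₁₈₀ + (k/22)(U₁₈₀ − S₁₈₀).
- Difference = (S₁₈₀ − S₉₀) + (k/22)(U₁₈₀ − S₁₈₀).

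The first term is change over time in the same subjects. The second is purely a change of subjects. Its weight is 9/22 = 0.41 at k = 9 and 14/22 = 0.64 at k = 14. Each point by which the two groups differ at Day 180 thus moves the apparent change by 0.41 to 0.64 of a point. The documents contain no GRASSP results, so the size in GRASSP points is unknown.

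**6. Later visits.** This amendment change does not touch Days 180, 270 and 365. However, SAP 5.4 produces every table at an interim when Cohort 5 need only have completed Day 180. Days 270 and 365 could then hold as few as 22 − 4 = 18 subjects, a composition change of the same kind at the other end of the table.

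**The case against.** The strongest reply is that little rides on this. GRASSP is exploratory (SAP 4.3), no hypothesis is tested (SAP 5.2) and no comparison between visits is planned. SAP section 6 puts n in every continuous summary, so a Day 90 n of 8 to 13 would be visible. SAP 5.3 shows missing counts only where applicable, so it is not certain that unscheduled tests would be displayed as missing. Three of the four totals are given as change from baseline, which removes baseline differences between the groups. Day 30 results are not lost, because section 6 lists all recorded data and 6.3.5 lists GRASSP scores. On this view a footnote would do.

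Most of that stands, and it limits the priority. It does not remove the problem. The displayed n shows that subjects are absent, not that the schedule explains it. Change from baseline does not remove differences in recovery between earlier and later subjects. Qualitative prehension has no change from baseline at all.

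A reader might go further and infer that the Day 90 set is necessarily weighted towards Cohort 5, the higher dose or C4 injuries. The documents do not support that.
- **Cohort 5.** Protocol 3.1.2 requires at least 3 + 5 + 2 + 5 = 15 subjects before the first Cohort 5 subject, so Cohort 5 is almost certainly absent from the 12. But the 16th and 17th subjects could belong to Cohort 5 and could have passed Day 90 before the amendment took effect at their site. The contrast of 4/13 (31%) with 4/22 (18%) holds only if all four were tested at Day 90 and n is 13.
- **Dose.** Also at n = 13, the 2 × 10⁷ dose could make up as little as 6/13 (46%), no different from 10/22 (45%) overall.
- **C4.** Eligibility for C4 injuries began with Amendment 3, but nothing says that a C4 subject was enrolled.

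Nor do the visit means compare wholly different patients: the Day 90 subjects are a subset of those due at Day 180.

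**Conclusion.** The point holds as a low-to-moderate priority improvement. At least 9 of 22 efficacy subjects (41%), and plausibly up to 14 (64%), had no Day 90 GRASSP scheduled. The Day 90 summary therefore rests on about 8 to 13 later-enrolled subjects, and a Day 90 to Day 180 difference in the pooled means partly reflects who is included.

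The bound of 9 needs no assumption about dosing order. It does rely on the log's statement that the Day 90 test was added at Amendment 3. Earlier schedules are not in the documents, and Amendment 2 also revised the schedule of assessments. That GRASSP was due at Days 180 to 365 for the earliest subjects is likewise assumed. The upper figure of 14 supposes that none of the five other efficacy subjects dosed by the count of 17 was tested at Day 90 under the new version. The subset may hold a larger share of Cohort 5, high-dose or C4 subjects, but by how much is not established.

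**What to change.** In SAP 6.3.5 and Table 14.2.3:

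1. Report Day 90, and Day 30 where it was done under an earlier protocol version, only for subjects whose version scheduled the test. Give that number as the denominator and show the remaining subjects as not scheduled rather than missing.
2. Beside the Day 90 value, show the same subjects' Day 180 change from baseline. For qualitative prehension, which has no change from baseline, show their Day 180 score.
3. Base any statement about the time course on subjects with GRASSP at all the visits compared. At the interim this also covers Cohort 5 subjects who have not yet reached Days 270 and 365.

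The cost is a few lines of SAP text and extra columns in one exploratory table, with no new data. The drawback is smaller numbers in the early-visit columns.

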7. TESTING/QUALITY CONTROL PLAN AND SOFTWARE/SYSTEM

All statistical programs will be written in SAS® version 9.3. Statistical programs will be tested and reviewed for Quality Control (QC) by a second programmer/biostatistician not involved in the programming as per DP Clinical (DPC)'s standard operating procedure (SOP). In addition, DPC's SOP will be followed to ensure that the information is complete, consistent, and accurately reflects the data stored in Clinical Data Management System

(CDMS) database. Further all tables, listings, and figures (TLFs) will undergo a QC process by an independent biostatistician/programmer to ensure that the information is complete, consistent, and accurately reflects the data stored in CDMS.

7.1 Programming Specifications for TLFs

Appendix 1 provides a list of all the TLFs that are planned to be produced.

7.2 Formatting Conventions

The following formatting conventions will be used to output TLFs:

- TLFs are outputted by SAS Output Delivery System (ODS) into Rich Text File (RTF) format.
- Tables and Listings will include borders around all headings and data cells.
- Output will be in landscape orientation with margins of 1.5 inches on top, and 1 inch for right, left, and bottom.
- The default font to be in tables/listings/figures will be Courier New.
- Preferred and minimum font size:

Portion of Output	Preferred	Minimum
Page Header	10 pt	8 pt
Title	10 pt	8 pt
Column header	10 pt	8 pt
Cells	10 pt	8 pt
Footnote	10 pt	8 pt
Page Footer	10 pt	8 pt

- Data will be centered within columns when the maximum length of the data being displayed is less than or equal to the maximum width of the column heading. When the maximum length of the data being displayed exceeds the maximum width of the column heading, the data will be left-justified.
- Column headings should be in initial capital characters. For numeric variables, include "unit" in the column heading when appropriate.
- In figures, axes will be labeled appropriately.

7.3 Standard Text Conventions

7.3.1 Header

All output (table, listing, or figure) will have the following header:

[Sponsor Name]

Protocol: [Protocol Number] Page xx of XX

All output will have the date and time (date and time output was generated) and internal page number in the footer. Tables/Listings/Figures should be internally paginated (i.e., page numbers should appear sequentially within each output).

7.3.2 **Title**

At least three (3) lines, in general, will be reserved for the entire title.

- The first line is for the table/listing/figure number;
- The second line is for the actual title; and
- The third line is reserved for the analysis population descriptor.

All titles will be centered, as shown in the following example:

Table 14.3.2.1 Overall Incidence of Safety Events Safety Population

7.3.3 Footnotes

Unless otherwise specified, footnotes will appear on all pages within the tables and listings as follows:

• Footnotes will be in the format of "NOTE: followed by 2 spaces, then the footnotes", as shown in the following example:

Note: SD = Standard Deviation; SEM = Standard Error of the Mean.

- Each line of a complete footnote should end with a period.
- When an abbreviation (e.g. AE, SAE, etc.) appears first time in the whole set of TLFs for a study, a footnote should be provided at least once; and it is up to the study statistician, to decide whether there is a need to repeat the same footnote for the rest of TLFs.
- A footnote serves as a brief explanation/clarification/definition /concept of a flag symbol or a character, an abbreviation, a terminology, etc., that appears in or relates directly to the displayed content of a table/listing/figure.
- Footnotes will not contain detailed/technical elaboration of, for example, a mathematical/statistical formula, a statistical term/test, or an algorithm for deriving a parameter value, which should be addressed in the text of the SAP.
- All footnotes will be at the lowest line of the page immediately above the footer. There will be one space between the last footnote and the footer.
- For Tables, first footnote will provide source listings and/or analysis datasets names for cross-referencing.

7.3.4 Footer

The following footer should appear at the very bottom of each page of a table, a listing, or a figure generated in SAS in the lower left corner:

Program: PGNAME.sas; Creation Date and Time: MMDDDYYYY HH:MM Data Cutoff: DDMMMYY:HH:MM:SS – Listing Generated MMM DD, YYYY

Where PGNAME = SAS program name.

7.4 Statistical Conventions

7.4.1 Statistics Reported

• Unless otherwise specified, the mean and standard deviation (SD) will be displayed to one more decimal place than the original value, while minimum and maximum will be reported in the format of the original data, e.g.:

Original: xx

Mean and SD: xx.x

Minimum and maximum: xx

- Descriptive statistics in this template include: Mean, Median, Standard Deviation (SD), Standard Error of Mean (SEM), Minimum, Maximum, and N. In addition, 95% CI will be presented when appropriate.
- Unless specified in the actual TLF shells for a study, all percentages will be rounded to 1 decimal place in all tables/listings/figures. Rounding will take place after all calculations have been performed.
- Use of N versus n:

N = total number of subjects or subjects in the population.

n = total number of subjects or subjects in the specific category.

7.4.2 **SAS Procedure Output**

If appropriate, SAS procedure output may be formatted and saved as source for references and will be included in Appendix.

